**Table 4: Treatment Period Visit Windows**

Target Scheduled Visit	Target Study Day a	Analysis Window Study Day a	
		Low	High
Baseline b	1	See Section 4.7.2	
Week 2	15	2	22
Week 4	29	23	36
Week 6	43	37	50
Week 8	57	51	71
Week 12 c	85	72	92 c

a Study day will be calculated from first dose of study drug.  
b Baseline is defined in [Section 4.7.2](#).  
c LFC and cTI by MRI will have no upper limit on Week 12.

The follow up visit (Week 16) will not be windowed. As described in [Section 8.10.3.1](#), sensitivity analyses will be conducted including only Week 16 assessments which are at least 22 days from last dose.

#### 4.7.2. Definition of Baselines

The baseline value for statistical analyses of quantitative laboratory parameters is defined as the mean of all available evaluations, including any unscheduled or repeat assessments, prior to the first administration of study drug, unless otherwise specified. If there is only one evaluation prior to the first administration of study drug, then the available data from this evaluation will be used as the baseline value.

For glucose and lipid parameters, only assessments taken while fasting for at least 8 hours will be included in the baseline derivation.

The baseline value for analyses of qualitative parameters (e.g., normal/abnormal) is defined as the last evaluation prior to the first administration of study drug.

The baseline value for analyses of height, weight, body mass index (BMI), waist circumference, and electrocardiogram parameters is defined as the last evaluation prior to the first administration of study drug.

The baseline value for pharmacodynamic analytes is defined as the Week 0/Day 1 predose value.

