1.3. Schedule of Activities

	Screening	Treatment Period ^a						ET ^b	Follow-Up ^c	Notes
Visit	Screening	Week 0	Week 2	Week 4	Week 6	Week 8	Week 12		Week 16	
Study Day	-42 to Day -1	Day 1	15	29	43	57	85		113	Visit windows post-randomization through Week 12: ± 3 days from the specified study day. Visit window Week 16: 1 week prior/+2 days from the specified study day.
Procedures										
Written Informed Consent	X									Written informed consent may be obtained via telephone in accordance with Section 10.1.2 . Screening may be initiated via telephone.
Patient Fasting	X	X	X	X	X	X	X	X	X	Patients must be in fasted state for at least 8 hours prior to blood collection and study drug administration, where applicable.
Randomization		X								
Review Inclusion and Exclusion Criteria	X	X								Recheck clinical status before randomization and first dose of study drug.
Demographics	X									Includes age, sex, and race/ethnicity.
Height and Weight	X	X	X	X	X	X	X	X	X	Height and weight are collected at Screening and will be used to calculate BMI for eligibility. Waist circumference is also measured at Screening. Only weight is collected on other days indicated.
Medical History	X	X								Includes details of illnesses and allergies, date(s) of onset, whether condition(s) is currently ongoing, and medication history, including alcohol use.

	Screening	Treatment Period ^a						ET ^b	Follow-Up ^c	Notes
Visit	Screening	Week 0	Week 2	Week 4	Week 6	Week 8	Week 12		Week 16	
Study Day	-42 to Day -1	Day 1	15	29	43	57	85		113	Visit windows post-randomization through Week 12: \pm 3 days from the specified study day. Visit window Week 16: 1 week prior/+2 days from the specified study day.
Physical Examination	X	X	X	X	X	X	X	X	X	A complete physical examination will be performed at Screening and Week 16. A targeted physical examination will be performed at all other visits, as needed.
Vital Signs	X	X	X	X	X	X	X	X	X	Includes temperature, pulse rate, respiratory rate, and blood pressure.
Chemistry ^d	X	X	X	X	X	X	X	X	X	Specific analytes are listed in Appendix 1 . ALT and AST stability may be evaluated prior to randomization per Section 5 . Increased monitoring criteria for elevated ALT and/or AST above $2 \times$ Baseline or above $5 \times$ ULN for < 1 week is outlined in Appendix 3 . Refer to Appendix 5 for the eGFR formula, to be calculated by central lab.
Hematology ^d	X	X	X	X	X	X	X	X	X	Specific analytes are listed in Appendix 1 .

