Study drug administration including missed doses, delays, and overdoses, and study drug dispensing and accountability, calculated durations of exposure, and calculated compliances will be presented in by-patient data listings. Compliance with fasting conditions will be presented in a separate by-patient data listings.

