### **9.3. Clinical Safety Laboratory Evaluations**

All laboratory assessments are specified in Appendix 1 of the study protocol. Laboratory parameters will be summarized in conventional units. Coagulation parameters, hemoglobin A1c, direct bilirubin, and indirect bilirubin will not be summarized.

Quantitative serum chemistry, fasting lipids, and hematology results will be summarized by treatment group using descriptive statistics at baseline and at each post-baseline visit. The change and percent change from baseline will also be summarized.

Values determined to be erroneous will be documented in the trial master file and analysis data reviewer’s guide. Erroneous values will not be included in summary tables or analyses but will be included in patient listings.

All clinical safety laboratory data will be presented in by-patient data listings. A separate listing for central laboratory normal ranges, by lab category, lab test, lab parameter, sex, and age, will be presented. Any local laboratory normal ranges for COVID-19 will be presented separately.

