### 9.3.3. Shifts in CTCAE Grade

Quantitative laboratory tests will be assigned grades based on National Cancer Institute Common Terminology Criteria for Adverse Events (NCI CTCAE) Version 5. Shifts in CTCAE grade of laboratory tests will be presented from baseline to worst post-baseline value. Summaries will present the number and percentage of patients with shifts in laboratory grade by treatment group. Denominators for percentages will be the number of patients with non-missing data at the specific assessment and baseline.

Some lab tests include additional clinical criteria which cannot be determined programmatically. [Table 10](#) below specifies the grade with clinical criteria in italics. The text in italics will not be considered when assigning grades programmatically.

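### The 8-hour fasting rule for glucose and lipids covers baseline only, so a non-fasting later value can enter the change summaries against a fasting-only baseline

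*SAP*

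**What the plan says.** SAP 4.7.2 averages all pre-dose evaluations of a quantitative laboratory test, including unscheduled and repeat ones, to form the baseline. It then adds one restriction, for glucose and lipids: "only assessments taken while fasting for at least 8 hours will be included in the baseline derivation".

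After baseline, four SAP provisions use these tests:

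- **SAP 9.3:** "Quantitative serum chemistry, fasting lipids, and hematology results will be summarized by treatment group using descriptive statistics at baseline and at each post-baseline visit". It continues: "The change and percent change from baseline will also be summarized". Glucose belongs to the clinical chemistry panel (Protocol Appendix 1, Table 2). The only values excluded are those judged erroneous.
- **SAP 4.7.1:** unscheduled and early-termination assessments are assigned to visit windows. Where a window holds several values, the one nearest the target day is analysed, or the later one if they tie.
- **SAP 9.3.1:** a treatment-emergent abnormality is a worsening of at least 2 CTCAE grades after baseline through Week 16.
- **SAP 9.3.3:** "Shifts in CTCAE grade of laboratory tests will be presented from baseline to worst post-baseline value".

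None of the four mentions fasting status as a condition. SAP 9.1 adds: "Compliance with fasting conditions will be presented in a separate by-patient data listings".

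The Protocol 1.3 Schedule of Activities marks fasting at Screening, every treatment visit, early termination and Week 16: "Patients must be in fasted state for at least 8 hours prior to blood collection and study drug administration, where applicable".

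**The concern.** The baseline rule shows that the authors expected some samples to be non-fasting and judged them unsuitable for glucose and lipids. Fasting is required before baseline samples just as it is later, and a filter was still thought necessary there. Without the same filter after baseline, the two sides of a change from baseline are defined differently. One is fasting by construction and the other is whatever was drawn.

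Protocol 9.4.2 places changes from baseline and grade shifts under the primary endpoint, and treatment-emergent laboratory abnormalities are part of that endpoint. Each dose group has about 20 patients, so a few such values can be visible in a by-visit mean. If the gap is noticed only after unblinding, any exclusion of individual values becomes a post-hoc decision.

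**Working it through.** The documents state no figure on this point, so there is none to reproduce. The check has four steps.

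**1. Is there a fasting condition anywhere after baseline?**

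| Use of the value | SAP section | Fasting condition |
|---|---|---|
| Baseline, glucose and lipids | 4.7.2 | Yes, at least 8 h |
| By-visit value, change, percent change | 9.3 | None for glucose; for lipids only the label *fasting lipids* |
| Choice among several values in a window | 4.7.1 | None |
| Treatment-emergent abnormality | 9.3.1 | None |
| Worst-grade shift | 9.3.3 | None |

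The label *fasting lipids* matches the name of the panel in Protocol Appendix 1 (Fasting Lipid Profile). It can be read as a restriction, but it need not be, and it does not reach glucose. A correctly measured non-fasting value is not erroneous in any sense that the SAP gives.

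**2. Can a non-fasting value displace a fasting one?** Protocol 8.1.7 asks for certain clinically significant abnormalities to be repeated within 48-72 hours and states no fasting condition for the repeat. Take Week 2, with target Day 15, an analysis window of Days 2-22 and a protocol visit allowance of ±3 days:

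- Scheduled visit on Day 12: distance 15 − 12 = 3 days. A repeat 48-72 h later falls on Day 14 or 15, at distance 1 or 0. The repeat is analysed.
- Scheduled visit on Day 14: distance 1. A repeat on Day 16 also has distance 1. The tie goes to the later value, so the repeat is analysed.

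Displacement follows from the rules as written. How often it would occur is not known.

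**3. How many patients could have such a value?** Inputs are the scheduled post-baseline visits in Protocol 1.3. Glucose has k = 6 (Weeks 2, 4, 6, 8, 12, 16). Lipids have k = 2 (Weeks 6 and 12; early termination also draws lipids). The per-visit non-fasting rate p is an assumption, taken as independent across visits. The chance of at least one non-fasting scheduled sample is 1 − (1 − p)^k.

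| p (assumed) | Glucose, k = 6 | Of 80 patients | Lipids, k = 2 | Of 80 patients |
|---|---|---|---|---|
| 1% | 1 − 0.99^6 = 5.9% | 4.7 | 1 − 0.99^2 = 2.0% | 1.6 |
| 2% | 1 − 0.98^6 = 11.4% | 9.1 | 1 − 0.98^2 = 4.0% | 3.2 |
| 5% | 1 − 0.95^6 = 26.5% | 21.2 | 1 − 0.95^2 = 9.8% | 7.8 |
| 10% | 1 − 0.90^6 = 46.9% | 37.5 | 1 − 0.90^2 = 19.0% | 15.2 |

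Unscheduled and repeat draws are not counted here. Repeated lapses by the same patients would break independence and lower these figures.

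**4. What would this do to a by-visit mean?** If a fraction p of values at a visit is raised by an amount d through recent food, the mean change moves by p × d. At p = 1% to 10% that is 0.01d to 0.10d. In a group of 20, a single such value moves the mean by d/20 = 0.05d. The documents give no value for d.

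**The case against.** The strongest reply is that the protocol already deals with this at collection. Fasting is required at every scheduled visit (Protocol 1.3, repeated in 5.3.2). Treatment-period chemistry and lipid samples are taken pre-dose, and dosing itself needs an 8-hour fast. A non-fasting value can then come only from non-compliance or from an unscheduled or repeat draw. This stands, and it is why the effect is probably modest. It does not remove the inconsistency, because the baseline samples are under the same requirement and were still given a filter.

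A reader might infer that non-fasting values inflate the worst-grade shifts and treatment-emergent abnormalities. The documents do not show this. The only glucose grade printed in the SAP is for hypoglycaemia (Table 10), which a recent meal would not be expected to worsen. Table 10 covers only tests with clinical criteria, so it does not prove that high glucose or lipids go ungraded, but no such grade appears. A counted abnormality also needs a worsening of at least 2 grades.

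A reader might also infer that non-fasting values should be dropped from all safety tables. That could hide a real event, such as a Grade 4 hypoglycaemia found at an unscheduled draw. Keeping every value in a worst-case search is a defensible conservative choice.

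Finally, the SAP 9.1 listing appears among exposure and dosing outputs and may describe fasting before dosing. It does not establish that fasting status is recorded for every blood draw.

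**Conclusion.** The point holds for the by-visit value, change and percent-change summaries and for the choice of value within a window. Glucose is clearly affected. Lipids are affected unless *fasting lipids* is meant as a restriction.

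The size is unknown. The range of 6% to 47% of patients for glucose and 2% to 19% for lipids rests on an assumed, independent per-visit rate of 1% to 10%. It counts patients with at least one non-fasting scheduled sample. It is not the chance that such a sample is the patient's worst value or alters a grade.

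The documents do not support saying that a drug-placebo difference would be obscured. SAP section 9 plans no inferential safety comparison unless otherwise specified, the sample size has no power basis, and randomisation should make the non-fasting rate similar across arms. The expected harm is some distortion of within-arm changes and some added noise in outputs that belong to the primary safety endpoint.

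**What to change.** Before unblinding, amend the SAP as follows:

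1. In 9.3, apply the 8-hour fasting condition to post-baseline glucose and lipid values in the by-visit value, change and percent-change summaries.
2. In 4.7.1, for glucose and lipids, choose only among fasting values when a window holds more than one.
3. In 9.3.1 and 9.3.3, keep all values. Flag non-fasting ones there and in the listings, and repeat these tables for glucose and lipids with fasting values only.
4. Confirm that the fasting status needed for the baseline rule is also recorded at post-baseline draws, including unscheduled ones, and state how an unknown status is handled.

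The cost is a few SAP sentences, one extra set of tables, and a few values lost from the by-visit summaries. No safety value leaves the grading tables.

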#### 4.7.3. Definition of End of Treatment

The End of Treatment value will be defined as the Week 12 value, either scheduled or windowed per [Table 4](#). If a Week 12 value is not available, the last non-missing on or before the last dose date will be used.

## 5. ANALYSIS SETS

Table 5 defines the analysis sets to be used.

**Table 5: Analysis Sets**

Analysis Sets	Description
Screened	All patients who sign the informed consent form (ICF).
Randomized	All patients randomized into any one of treatment groups. Treatment assignment will be based on the randomized treatment.
Pharmacokinetic (PK)	All randomized patients who received at least 1 dose of TERN-201 and have evaluable PK data. Evaluable PK data is defined in Section 8.7 .
Pharmacodynamic (PD)	All randomized patients who received at least 1 dose of study drug (TERN-201 or placebo) and for whom at least one post baseline assessment of VAP-1/SSAO activity and methylamine is available. Treatment assignment will be based on the treatment actually received.
PK/PD Substudy	All patients who consented to the PK/PD substudy, were randomized into the PK/PD substudy, and received at least 1 dose of study drug (TERN-201 or placebo). Treatment assignment will be based on the treatment actually received.
Safety	All patients who received at least 1 dose of study drug. Treatment assignment will be based on the treatment actually received.
Efficacy	All randomized patients who received at least 1 dose of study drug. Treatment assignment will be based on the randomized treatment.
Per Protocol (PP)	All randomized patients who have completed the study without any major protocol deviations. Treatment assignment will be based on the treatment actually received.
Treatment Completer	All patients who complete 12 weeks of treatment with at least 80% compliance based on study drug accountability. Treatment assignment will be based on the randomized treatment.

## 6. EXAMINATION OF SUBGROUPS

No analyses based on subgroups will be conducted.

## 7. STUDY POPULATION

### 7.1. Patient Disposition

Patient disposition will be summarized for the Screened Analysis Set by treatment group and overall total. The summary will include:

- Number of patients screened.
- Number of screen failures, i.e., screened but not randomized, with reasons for screen failure. The denominator for percentage of screen failures will be the number of patients screened. The denominator for percentages for reasons for screen failures will be the number of screen failures.
- Number randomized. The denominator for percentage of randomized patients will be the number of patients screened.
- Number randomized and not treated. The denominator for percentage of randomized and not treated patients will be the number of patients randomized.
- Number in each analysis set. The denominator for percentage in each analysis set will be the number of randomized patients.
- Number who discontinued treatment early and reason(s) for discontinuation of treatment. The denominator for percentages will be the number of randomized and treated patients (Efficacy Analysis Set).
- Number who discontinued from study prior to completing the study and reason(s) for discontinuation. The denominator for percentages will be the number of randomized and treated patients (Efficacy Analysis Set).

A by-patient data listing of study disposition information including the reasons for treatment and/or study termination will be presented for the Safety Analysis Set. Withdrawal of consent details will also be included, if applicable.

A by-patient data listing including the reasons for exclusion from each analysis set will be presented.

### 7.2. Demographics and Baseline Characteristics

Demographic variables will include the following:

- Age at informed consent including the subgroup of <65 years vs  $\geq 65$  years
- Sex
- Race
- Ethnicity

Other baseline characteristics will include the following:

- Weight (kg)
- Height (cm)

- BMI ( $\text{kg}/\text{m}^2$ ) including the following subgroup:  $<30$ ,  $\geq 30$  -  $<35$ ,  $\geq 35$  -  $<40$ ,  $\geq 40$   $\text{kg}/\text{m}^2$
- Waist circumference (cm)
- Baseline liver stiffness by transient elastography (kPa)
- Baseline Controlled Attenuation Parameter by transient elastography (CAP; dB/m)
- Baseline LFC (%) by MRI-PDFF
- Baseline cTI (msec) by MRI including the following subgroup: Elevated ( $>800$  –  $900$  msec) and High ( $>900$  msec)
- Liver biopsy within 2 years of randomization
  - Baseline fibrosis stage (F1, F2, F3)
  - Baseline NAFLD Activity Score (NAS)
- Baseline comorbidities will be based on Medical History case report form, Medical Dictionary of Regulatory Activities (MedDRA) preferred term (PT)
  - Diabetes status (yes, no) will be defined as PT preferred term (PT) includes “Diabetes mellitus” or “Diabetic neuropathy” will be assigned yes, otherwise no.
  - Hypertension (yes, no) will be defined as PT of “Hypertension” will be assigned yes, otherwise no.
  - Dyslipidemia (yes, no) will be defined as Standardized MedDRA query (SMQ) of “Dyslipidemia (SMQ)” will be assigned yes, otherwise no.
- Baseline medication use, defined as starting prior to first administration of study drug, regardless of end date:
  - Statins defined by the WHODD Standardized Drug Grouping (SDG) of “Statins”
  - Antihypertension medications defined by the WHODD SDG of “Antihypertensives”
  - Antithrombotic medications defined by WHODD SDG of “Antithrombotic drugs”
  - Antidiabetic medications defined by the WHODD SDG of “Drugs used in diabetes”

The following baseline laboratory tests will be summarized as continuous variables and as frequencies for categorizations described:

- Baseline plasma VAP-1/SSAO activity
- Baseline soluble VAP-1 (sVAP-1) concentration
- Baseline ALT level:
  - $\leq 60$  U/L versus  $>60$  U/L (overall and by sex)
- Baseline AST level: The same subgroups as specified for ALT above will be used.
- Baseline GGT level:  $\leq \text{ULN}$ ,  $>\text{ULN}$
- Baseline ALP level:  $\leq \text{ULN}$ ,  $>\text{ULN}$

- Baseline total bilirubin level:  $\leq$ ULN,  $>$ ULN
- Screening HbA1c:  $<$  7%,  $\geq$  7%
- Baseline platelet count:  $\leq$ ULN,  $>$  ULN

Demographics and baseline characteristics will be summarized by treatment group and overall, for Efficacy, Safety, PP, and Treatment Completer Analysis Sets. The Safety, PP, and Treatment Completer Analysis Sets will only be presented if the analysis set differs from the Efficacy Analysis Set by more than 10% total.

All demographic and baseline characteristics data will be presented in by-patient data listings using the Efficacy Analysis Set.

No inferential statistical comparisons will be performed.

### **7.3. Protocol Deviations**

Protocol deviations will be identified and documented in the clinical trial management system (CTMS). Major protocol deviations that could potentially affect the conclusions of the study will be identified prior to database lock and unblinding of individual patient treatment information.

Major protocol deviations include, but are not limited to

- Patients who entered the study even though they did not satisfy the entry criteria.
- Patients who developed withdrawal criteria during the study but were not withdrawn.
- Patients who received the wrong treatment or were dispensed an incorrect dose.
- Patients who received an excluded concomitant treatment.

All major protocol deviations will be summarized by treatment group and overall total for each deviation category using the Efficacy Analysis Set.

All protocol deviations and separately only major protocol deviations will be presented in a by-patient data listing. A separate listing for COVID-19 protocol deviations will be presented.

### **7.4. General Medical History**

All medical history conditions will be coded using the Medical Dictionary of Regulatory Activities (MedDRA). Medical history will be summarized by treatment group and overall total, by system organ class and preferred term, using the Safety Analysis Set. Summaries will be ordered by descending order of the overall total incidence of system organ class and preferred term within each system organ class.

### **7.5. Prior and Concomitant Medications**

Prior medications are defined as medications that started before first study drug administration and either stopped before or continued after first study drug administration. Concomitant medications are defined as medications that are being taken while on study drug. Medications that are ongoing on the date of the first administration of study drug will be classified as both prior and concomitant. Any medication that cannot be confirmed as stopping before the start of

study drug will be classified as both a prior and a concomitant medication. Imputation of partial dates is defined in [Appendix 2](#).

Prior and concomitant medications will be summarized separately and the number and percentage of patients in each treatment group who took at least one prior (concomitant) medication as well as the number and percentage of patients who took each type of medication will be summarized by Anatomic Therapeutic Class (ATC) Level 2, ATC Level 4, and preferred name for the Safety Analysis Set. If a patient has more than one occurrence of the same preferred name, then the preferred name will be counted only once for that patient. Similarly, if a patient has more than one preferred name within ATC Level 4 or ATC Level 4 within ATC Level 2, then the patient will be counted only once in that ATC Level 4 or ATC Level 2.

